3.6. Missing Data and Outliers

3.6.1. Missing Data

In general, missing data will not be imputed unless methods for handling missing data are specified. Exceptions are presented in this document.

Imputation rules for missing date of birth are described in Section 3.7. For missing last dosing date of study drug, imputation rules are described in Section 5.2.1. The handling of missing or incomplete dates for initial AML diagnosis is described in Section 5.4, for date of death and the start date of new anti-AML therapy in Section 6.2.1, for AE onset in Section 7.1.5.2, and for prior and concomitant medications in Sections 5.10.1 and 5.10.2, respectively.

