6.2. Secondary Efficacy Endpoints

6.2.1. Definition of Secondary Efficacy Endpoints

The secondary efficacy endpoints are as follows:

- ORR (Cohorts 1 and 2): The ORR is the proportion of patients who achieve CR (CR_{MRD}- or CR_{MRD+/unk}), CRi, CRh, PR, or MLFS as determined by the investigator based on prespecified criteria (Appendix 2) while on study prior to initiation of any new anti-AML therapy (including SCT).
- CR/CRi Rate (Cohorts 1 and 2): The CR/CRi rate is the proportion of patients who achieve CR (CR_{MRD}- or CR_{MRD+/unk}) or CRi as determined by the investigator based on prespecified criteria (Appendix 2) while on study prior to initiation of any new anti-AML therapy (including SCT).
- CR_{MRD}– Rate (Cohorts 1 and 2): The CR_{MRD}– rate is the proportion of patients who achieve a CR_{MRD}– as determined by the investigator based on prespecified criteria (Appendix 2) while on study prior to initiation of any new anti-AML therapy (including SCT).
- CR/CRh Rate (Cohorts 1 and 2): The CR/CRh rate is the proportion of patients who achieve CR (CR_{MRD}- or CR_{MRD+/unk}) or CRh as determined by the investigator based on prespecified criteria (Appendix 2) while on study prior to initiation of any new anti-AML therapy (including SCT).
- cCR Rate (Cohorts 1 and 2): The cCR rate is the proportion of patients who achieve cCR determined by investigator based on the prespecified criteria (Appendix 2) while on study prior to initiation of any new anti-AML therapy (including SCT).
- DOR (Cohorts 1 and 2): The DOR is measured from the time assessment criteria are met for CR (CR_{MRD}- or CR_{MRD}-/_{unk}), CRi, CRh, PR, or MLFS, whichever is first recorded, until the first date of AML relapse, progressive disease, or death (including assessments post SCT). Those who are not observed to have a relapse, progressive disease, or death will be censored at the date of their last response assessment. If patients start taking new anti-AML therapies (except SCT and post SCT maintenance treatment) before relapse/PD/death, duration of response will be censored at the last response assessment before the initiation of the new anti-AML therapies.

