- Duration of CR (Cohorts 1 and 2): The duration of CR is measured from the time the assessment criteria are first met for CR (CR_{MRD} or CR_{MRD+/unk}) until the first date of AML relapse or death (including assessments post SCT). Those who are not observed to have relapsed disease or death will be censored at the date of their last response assessment. If patients start taking new anti-AML therapies (except SCT and post SCT maintenance treatment) before relapse/death, duration of CR will be censored at the last response assessment before the initiation of the new anti-AML therapies.
- Duration of CR/CRi (Cohorts 1 and 2): The duration of CR/CRi is measured from the time the assessment criteria are first met for CR (CR_{MRD} or CR_{MRD}) or CRi until the first date of AML relapse or death (including assessments post SCT). Those who are not observed to have relapsed disease or death will be censored at the date of their last response assessment. If patients start taking new anti-AML therapies (except SCT and post SCT maintenance treatment) before relapse/death, duration of CR/CRi will be censored at the last response assessment before the initiation of the new anti-AML therapies.
- Duration of CR/CRh (Cohorts 1 and 2): The duration of CR/CRh is measured from the time the assessment criteria are first met for CR (CR_{MRD} or CR_{MRD+/unk}) or CRh until the first date of AML relapse or death (including assessments post SCT). Those who are not observed to have relapsed disease or death will be censored at the date of their last response assessment. If patients start taking new anti-AML therapies (except SCT and post SCT maintenance treatment) before relapse/death, duration of CR/CRh will be censored at the last response assessment before the initiation of the new anti-AML therapies.
- EFS (Cohorts 1 and 2): EFS is defined as the time from the date of the first dose of study treatment to the earliest date of documented relapse from CR, treatment failure (TF) defined as failure to achieve CR during the response assessment window (the first treatment dosing date until before the fifth cycle of magrolimab+venetoclax+azacitidine in Cohort 1 and the first treatment dosing date until before the third cycle of magrolimab + MEC in Cohort 2), or death from any cause. Response assessments post SCT or new anti-AML therapies will be excluded from deriving treatment failure. Table 6-1 summarizes the details of the EFS derivation algorithm.

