- Platelet Transfusion Independence Rate: The platelet transfusion independence rate is the proportion of patients who have a 56-day or longer period with no platelet transfusions at any time between the date of the first dose and discontinuation of study treatment among all patients who are platelet transfusion-dependent at baseline, defined as having received a platelet transfusion within the 28 days prior to the first dose of study treatment (conversion rate), and among all patients who are platelet transfusion independent at baseline (maintenance rate).

The date of the last known alive will be determined by selecting the last available visit date, including unscheduled visits, across all datasets.

Every attempt will be made to ensure that complete death dates are recorded. In those rare instances where complete death dates are not recorded, the following algorithm will be used:

- If day is missing but the month and year are available, then the imputed date will be the first day of the month or the last known alive date + 1, whichever is later.
- If day and month are missing but year is available, then the imputed date will be 01Jan of that year or the last known alive date + 1, whichever is later.

When the date of initiation of a new anti-AML therapy/SCT other than the study treatment is incomplete or missing, the following algorithm will be followed:

- If the day is missing but the month and year are available, then the imputed day will be the first day of the month or last dose date of study drug +1, whichever is later.
- If day and month are missing but year is available, then the imputed day and month will be 01Jan, first dose date of study drug +1, or the last day of the month for the last adequate disease assessment if they have the same year, whichever is later.

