7.1.5. Treatment-Emergent Adverse Events

7.1.5.1. Definition of Treatment-Emergent Adverse Events

Treatment-emergent adverse events (TEAEs) are defined as any AEs with an onset date on or after the study drug start date and no later than 70 days after the study drug last dosing date or the day before initiation of new anticancer therapy including SCT, whichever comes first.

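### When only the day of a new anti-AML therapy is missing, the imputed start can fall before a relapse dated in the same month, and DOR and the CR-duration endpoints then censor that observed relapse

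*SAP*

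**What the plan says.** SAP Section 6.2.1 has two rules for an incomplete start date of new anti-AML therapy or SCT.

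- Day missing, month and year known: "then the imputed day will be the first day of the month or last dose date of study drug +1, whichever is later".
- Day and month missing, year known: the latest of "01Jan, first dose date of study drug +1, or the last day of the month for the last adequate disease assessment", where the last of these applies if the years agree.

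Section 3.6.1 names Section 6.2.1 as the place where this date is handled: "for date of death and the start date of new anti-AML therapy in Section 6.2.1".

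The date matters for the duration endpoints in the same section. If a patient starts a new therapy other than SCT or post-SCT maintenance, then for DOR: "before relapse/PD/death, duration of response will be censored at the last response assessment before the initiation of the new anti-AML therapies". For duration of CR: "before relapse/death, duration of CR will be censored at the last response assessment before the initiation of the new anti-AML therapies". Durations of CR/CRi and CR/CRh follow the same rule.

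EFS works differently. In Table 6-1, a patient who reached CR within the window has an event at relapse or death, and new therapy does not censor.

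**The concern.** The day-missing rule picks the earliest date that fits the known month and lies after the last dose. New therapy for AML is commonly given because of relapse, and both can fall in one calendar month. The imputed start can then land before the relapse that led to the therapy. In the data the relapse follows new therapy, so the duration rules discard it and censor the patient at an earlier response assessment.

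For these endpoints the error has one direction: an observed event is removed and the Kaplan-Meier curve is raised. The censoring is also informative, since it occurs in patients because they relapsed.

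The next bullet, for a date known less completely, is anchored to the last adequate disease assessment. The poorer date can therefore give the better answer.

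**Working it through.** The SAP states no figure on this point, so there is none to reproduce. The check applies the rule as written.

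**Rule.** Imputed start = max(1st of the therapy month, last dose + 1). A relapse is lost when the imputed start is strictly before the relapse date.

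**Conditions for loss.** Both terms of the maximum must precede relapse.

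1. The 1st of the therapy month precedes relapse only if relapse is in that month and not on the 1st.
2. Last dose + 1 precedes relapse only if the last dose was at least 2 days before relapse.
3. The therapy must not be SCT or post-SCT maintenance, which the duration endpoints exempt.

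**Worked example (assumed dates).** Last dose 24 February 2022, relapse marrow 10 March, true therapy start 20 March.

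| Information on therapy date | Imputed start | Relapse of 10 March |
|---|---|---|
| Month and year | max(1 March, 25 February) = 1 March | Censored |
| Year only, first dose 1 June 2021, relapse marrow as last adequate assessment | max(1 January 2022, 2 June 2021, 31 March 2022) = 31 March | Event |

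**Cases where nothing is lost.**

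- Last dose 14 March, relapse 10 March, therapy in March: imputed start 15 March, after relapse.
- Last dose 15 March, relapse 28 March, therapy in April: imputed start 1 April, after relapse.

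**How often, given a missing day and a last dose at least 2 days before relapse.** Let g be the days from relapse to true therapy start (an assumption) and L the length of the therapy month. Relapse falls on day 2 or later of that month for L − 1 − g of the L possible start days, so the share is (L − 1 − g)/L, or zero if that is negative. Over a 365-day year, for gaps of up to 27 days, this is 1 − 12(1 + g)/365:

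| g (days) | Calculation | Share of relapses censored |
|---|---|---|
| 3 | 1 − 48/365 | 87% |
| 7 | 1 − 96/365 | 74% |
| 14 | 1 − 180/365 | 51% |
| 21 | 1 − 264/365 | 28% |
| 28 | (7 × 2 + 4 × 1 + 0)/365 | 5% |
| 35 | none possible | 0% |

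Listing every start date from 2021 to 2023 gives the same shares. They do not change for last doses 2, 7, 14 or 28 days before relapse. With the last dose 1 day before relapse, on the relapse date or after it, the share is 0%.

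**Weight of one record.** At the Cohort 2 planning values in Section 1.3, 35% × 36 = 12.6, or about 13 patients with CR. One lost relapse is 1/13, about 8% of the duration-of-CR sample. This is the weight of one patient, not an expected bias.

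**The case against.** The strongest reply is that an early start date is cautious where it matters most. The primary CR rate (Section 6.1.1) and the other response rates count only responses before new therapy, so an early date can only lower them. In EFS, new therapy within the window makes a patient without CR a treatment failure, which is also conservative. This stands: the rule inflates none of these, and OS is untouched. It does not help the four duration endpoints, where the same choice works in the favourable direction.

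A second reply is that the consequence is limited. Durations are descriptive Kaplan-Meier summaries (Section 6.2.2) in a proof-of-concept study, this SAP version serves a final synoptic CSR (Section 13), and analyses follow query resolution, so missing days may be few. Post-treatment therapies are also listed by patient (Section 5.11). This stands as a limit on size. It does not make the rule correct.

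Two stronger readings are tempting.

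- **That every day-missing record loses its relapse.** It does not. The conditions above must hold together, and a patient dosed up to the day before relapse is fully protected. Cohort 1 is treated until discontinuation criteria are met, so that case is plausible there.
- **That the treatment-emergent AE and laboratory windows are wrongly cut short and need a last-day-of-month date.** Those windows end 70 days after last dose "or the day before initiation of new anticancer therapy including SCT, whichever comes first". Section 6.2.1 speaks of anti-AML therapy or SCT, so applying its rule there is an inference through Section 3.6.1. AEs outside the window are still listed, with a treatment-emergence flag (Section 7.1.6.1). The last day of the month would only exchange one error for its mirror image. For a start day uniform in the month, the mean lead from the 1st and the mean lag to month end are both (L − 1)/2, about 14.7 days averaged over the year, before other bounds. The added days would fall after new therapy began. That is a trade-off, not a defect.

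**Conclusion.** The point holds in conditional form. As written, the day-missing rule can place a non-SCT new therapy before a relapse or progression already dated in the same month, and DOR and the durations of CR, CR/CRi and CR/CRh then censor an observed event. These durations are biased upward.

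The shares of 87%, 74%, 51% and 28% rest on a missing day, a last dose at least 2 days before relapse, dates spread evenly over the calendar, and assumed gaps of 3 to 21 days. They are shares of such records, not of all responders. If no record has a missing day, no result changes. With responder groups as small as those planned, a single record can be visible, and the year-only rule shows that the SAP already has a way to anchor this date to disease assessment.

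**What to change.** Add to the day-missing bullet in Section 6.2.1: if a relapse or progression is dated in the known month, the imputed start is the latest of the 1st of the month, last dose + 1, and the relapse or progression date + 1, not beyond the end of that month. In the worked example this gives max(1 March, 25 February, 11 March) = 11 March, and the relapse of 10 March stays an event. If relapse is on the last day of the month, the cap puts the start on the relapse date, which is not before it.

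Also list every patient whose DOR or CR-duration status depends on an imputed therapy date.

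The cost is one sentence, a few lines of code and one listing, using dates already collected. There is a small downside: if therapy truly began before the relapse in that month, one event is counted that would have been censored. No separate date rule is proposed for the safety windows.

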6.2.2. Analysis Methods for Secondary Efficacy Endpoints

The point estimates of the ORR, CR rate, CR/CRi rate, CR_{MRD} rate, cCR rate, and CR/CRh rate and the corresponding 2-sided exact 95% CIs based on the Clopper-Pearson method will be provided for Cohorts 1 and 2. The analyses of RBC and platelet transfusion independence rates (conversion rate and maintenance rate) will be similar to those of ORR.

Medians, first quartile (Q1), and third quartile (Q3) of EFS distribution, and the proportion of patients who are event free at Weeks 12, 24, and 48 from the first dosing date will be estimated by cohort using the KM method and the corresponding 95% CIs will be reported. Kaplan-Meier plots will be provided. Analyses of OS will be similar to those of EFS.

For the time-to-event endpoints of duration of CR, duration of CR/CRi, duration of CR/CRh, DOR, analyses will be conducted on the subsets for which the outcome measures are defined. Specifically, the duration of CR, duration of CR/CRi, duration of CR/CRh, and DOR will be based on patients in Cohorts 1 and 2 who achieve CR, CR/CRi, CR/CRh, and OR, respectively. The KM method will be used to estimate median durations and 95% CIs, and KM plots will be provided.

6.4. Changes From Protocol-Specified Efficacy Analyses

The following changes are made from the protocol-specified efficacy analyses:

- Analyses on Cohort 3 will not be conducted since no patients are enrolled in the cohort.
- Given the sample size calculation determined by patients in both Safety Run-in and Phase 2 in Cohorts 1 and 2 and all safety Run-in patients were dosed with the Recommended Phase 2 Dose for both cohorts 1 and 2, the Primary analysis of CR will be conducted on Patients in Cohorts 1 and 2, including patients in both Safety Run-in and Phase 2. Since the enrollment of Cohort 1 terminated earlier, and the number of patients enrolled in Cohort 1 is smaller than the sample size, hypothesis testing of CR rate in Cohort 1 will not be conducted.

7. SAFETY ANALYSES

7.1. Adverse Events and Deaths

All Adverse Events (AEs) will be listed. The focus of AE summarization will be on treatment-emergent adverse events (TEAEs).

7.1.1. Adverse Event Dictionary

Clinical and laboratory adverse events (AEs) will be coded using the current version of MedDRA. System organ class (SOC), high-level group term (HLGT), high-level term (HLT), preferred term (PT), and lower-level term (LLT) will be provided in the AE dataset.

7.1.2. Adverse Event Severity

Adverse events are graded by the investigator as Grade 1, 2, 3, 4, or 5 according to NCI CTCAE Version 5.0. The severity grade of events for which the investigator did not record severity will be categorized as "missing" for tabular summaries and data listings. The missing category will be listed last in summary presentation.

7.1.3. Relationship of Adverse Events to Study Treatment

Related AEs are those for which the investigator selected "Related" on the AE CRF to the question of "Related to Study Treatment." Relatedness will always default to the investigator's choice, not that of the medical monitor. Events for which the investigator did not record relationship to study drug will be considered related to study drug for summary purposes. However, by-patient data listings will show the relationship as missing.

7.1.4. Serious Adverse Events

Serious adverse events (SAEs) will be identified and captured as SAEs if the AEs met the definitions of SAEs that were specified in the study protocol. SAEs captured and stored in the clinical database will be reconciled with the SAE database from the Gilead Drug Safety and Public Health Department before data finalization.

7.1.5. Treatment-Emergent Adverse Events

7.1.5.1. Definition of Treatment-Emergent Adverse Events

Treatment-emergent adverse events (TEAEs) are defined as any AEs with an onset date on or after the study drug start date and no later than 70 days after the study drug last dosing date or the day before initiation of new anticancer therapy including SCT, whichever comes first.

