7.1.5.2. Missing or incomplete Dates

If the onset date of the AE is incomplete and the AE stop date is not prior to the first dosing date of study drug, then the month and year (or year alone if month is not recorded) of onset determine whether an AE is treatment emergent. The event is considered treatment emergent if both of the following 2 criteria are met:

- The AE onset is the same as or after the month and year (or year) of the first dosing date of study drug, and
- The AE onset date is the same as or before the month and year (or year) of the date corresponding to the cutoff date of TEAE period, which is defined as the 70 days after the study drug last dose date or the day before initiation of new anticancer therapy including SCT, whichever comes first.

An AE with completely missing onset and stop dates, or with the onset date missing and a stop date later than the first dosing date of study drug, will be considered to be treatment emergent. In addition, an AE with the onset date missing and incomplete stop date with the same or later month and year (or year alone if month is not recorded) as the first dosing date of study drug will be considered treatment emergent.

In case when the AE onset date is incomplete and needs to be imputed, the following algorithm will be followed:

- If the day is missing but the month and year are available, then the imputed day will be the first day of the month or the first dosing date if they have the same month and year, whichever is later.
- If the day and month are missing but year is available, then the imputed day and month will be 01Jan or the first dosing date if they have the same year, whichever is later.

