7.1.7. Additional Analysis of Adverse Events

7.1.7.1. Dose Limiting Toxicity

A DLT is defined as any Grade 4 or higher hematologic toxicity or Grade 3 or higher nonhematologic toxicity (that has worsened in severity from pretreatment baseline) during the 4-week DLT assessment period and is related to magnolimab or magnolimab combination.

For each cohort being evaluated for safety and tolerability based on DLT assessment, DLT evaluable patients are identified as those who either experienced a DLT any time during the DLT Assessment Period or completed at least certain amount of the drug administration during the DLT Assessment Period. A summary of DLT will be presented by Preferred Term and Severity.

A listing of the DLT AEs will be provided by cohort including cohort number, patient ID, actual dose amount prior to or on the start date of the AE, DLT term from investigator as well as CTCAE term and associated severity grade, if available.

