7.2.2.1. Treatment-Emergent Laboratory Abnormalities

Treatment-emergent laboratory abnormalities are defined as values that increase at least 1 toxicity grade from baseline at any postbaseline time point, up to and including the date of last dose of study drug plus 70 days or the day before initiation of any new anticancer therapy including SCT, whichever comes first. If the relevant baseline laboratory value is missing, any abnormality of at least Grade 1 observed within the time frame specified above will be considered treatment emergent.

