7.7. Changes From Protocol-Specified Safety Analyses

The following changes are made from the protocol-specified safety analyses:

- AEs occurring one day before initiation of new anticancer therapy (including SCT) is added in TEAE definition to be aligned with magrolimab studies.
- AEs occurring within the date of last dose of study drug plus 70 days or the day before initiation of new anticancer therapy (including SCT) is added in TE lab abnormality definition to be aligned with TEAE definition change.

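### SAP 7.1.5.1 defines a TEAE by onset date alone, so an AE known to predate first dose that worsens on treatment is left out of the TEAE tables if it stays on one record

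*SAP*

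**What the plan says.** Section 7.1.5.1 sets two conditions for a TEAE, both on the onset date. The start condition is "defined as any AEs with an onset date on or after the study drug start date". The end condition is "no later than 70 days after the study drug last dosing date or the day before initiation of new anticancer therapy including SCT", whichever is earlier. Grade plays no part.

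Section 7.1.5.2 deals with missing and partial dates only. Section 7.1.6 builds the AE summary tables on TEAEs: overall, Grade 3 or higher, serious, treatment-related, leading to discontinuation, interruption or dose reduction, and leading to death. Section 7.1.7.3 does the same for the AEs of interest. Section 7.7 lists the departures from the protocol's safety analyses, and for TEAEs it changes only the end of the window.

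Two other safety definitions in the SAP do use worsening. A DLT under 7.1.7.1 is a toxicity "that has worsened in severity from pretreatment baseline) during the 4-week DLT assessment period". A treatment-emergent laboratory abnormality under 7.2.2.1 consists of "values that increase at least 1 toxicity grade from baseline at any postbaseline time point".

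**The concern.** Patients starting treatment for AML may already have anaemia, infection, fever or bleeding. If such a condition is held as an AE with a pre-dose onset and rises to Grade 3 or higher on study drug, the toxicity of interest is the on-treatment rise. Read literally, 7.1.5.1 leaves that event out of every TEAE table because it began too early.

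DLTs and treatment-emergent AEs are both primary safety endpoints of the run-in cohorts (Sections 1.1.1 and 1.1.2), so one event could count for one and not for the other. No cohort has a control arm (Section 1.2), so any omission goes directly into the reported absolute rate.

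**Working it through.** The SAP gives no figure to reproduce. The check is a comparison of rules, followed by arithmetic for scale.

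**1. One event under each rule.** Take a related nonhaematologic AE that starts at Grade 1 before first dose and reaches Grade 3 during the DLT period.

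| How the event is held | Rule | Result |
|---|---|---|
| One record, known pre-dose onset | DLT, 7.1.7.1 | Counts: Grade 3 and worsened |
| One record, known pre-dose onset | TEAE, 7.1.5.1 | Does not count |
| One record, onset missing, stop after first dose | 7.1.5.2 | Counts |
| One record, partial onset in the same month and year as first dose, stop not before first dose | 7.1.5.2 | Counts |
| New record opened at the grade increase | 7.1.5.1 | Counts |

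The third row rests on the wording that an AE with "the onset date missing and a stop date later than the first dosing date of study drug, will be considered to be treatment emergent". A fully documented early onset is therefore handled less conservatively than a missing one.

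**2. Do other rules restore the event?** The highest-severity rule in 7.1.6.1 works within the summaries and cannot bring back an event already excluded. The listings cover all AEs, all SAEs and all AEs of Grade 3 or higher, but give no incidence, and their treatment-emergent flag follows the same onset rule. Grade and shift tables (7.2.2.2, 7.2.3) capture worsening cytopenias. They do not capture serious infection, haemorrhage, pneumonitis or thromboembolism. Section 7.1.7.4 speaks of AEs rather than TEAEs, so its tables by preferred term may not be restricted, but 7.1.6.1 brings the same topics into its TEAE summaries.

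**3. Weight of one patient.** The planned Cohort 2 size is 36 (Section 1.3), so 1/36 = 2.8 percentage points. An assumed 0 to 4 affected patients with no other qualifying event gives 0 to 4/36 = 11.1 points. Cohort 1 was planned at 46 and enrolled fewer (Section 6.4), so one patient there weighs more than 1/46 = 2.2 points.

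**4. Expected loss under assumptions.** None of these inputs is in the SAP. Let *a* be the share of patients with an AE ongoing at first dose, *w* the share of those who worsen to Grade 3 or higher on the same record, and *p* the chance that such a patient has another TEAE of Grade 3 or higher (taken as independent). Patients are counted once, so the loss in the overall Grade 3 or higher row is a × w × (1 − p), and a × w is its upper bound.

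| a, w | p = 0 (bound) | p = 0.5 | p = 0.9 |
|---|---|---|---|
| 10%, 10% | 1.0% | 0.5% | 0.1% |
| 20%, 25% | 5.0% | 2.5% | 0.5% |
| 30%, 40% | 12.0% | 6.0% | 1.2% |

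The middle row, in patients of 36, is 0.05 × 36 = 1.8, then 0.9, then 0.18. All entries are zero if a grade increase opens a new record.

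**The case against.** The strongest objection is that how a worsening AE is recorded is usually fixed in the protocol or the CRF instructions, which are not at hand. If each grade increase is a new record, or a condition held as medical history (Section 5.4) becomes an AE only when it worsens, then onset falls on treatment and 7.1.5.1 already counts it. The DLT listing in 7.1.7.1 hints at this, since it shows the dose given up to the start date of the AE, which presupposes an on-treatment start. This stands. A reader might infer that a worsened event is never treatment-emergent and that severe toxicity is in fact under-counted. The SAP supports neither statement.

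A reader might also take 7.7, where the laboratory rule was changed "to be aligned with TEAE definition change", as a promise that the two definitions match on worsening. It is not: that entry concerns only the end of the window. Laboratory values are serial measurements with no onset field, so a baseline comparison is natural for them. The difference is a misalignment, not a contradiction.

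Other outputs limit the consequences. All deaths are tabulated regardless of TEAE status (7.1.6.1, 7.1.6.2), DLTs have their own summary, and laboratory worsening is graded separately. This also stands.

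The objection does not remove the point that 7.1.5.1 states a rule. The rule is complete as written, contains no worsening criterion, and would be programmed that way.

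**Conclusion.** The point holds in conditional form. As written, an AE with a known pre-dose onset that increases in CTCAE grade on treatment is not a TEAE if it stays on one record. The same toxicity can meet the DLT definition and still be missing from the TEAE, Grade 3 or higher, serious and AE-of-interest tables.

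The size cannot be derived from the SAP. It is zero if worsening always opens a new record. Otherwise it is 2.8 points for each affected patient without another qualifying event, at the planned Cohort 2 size. The percentages in step 4 of the working rest on assumed inputs and show scale only. The point deserves a change because the remedy is cheap and does nothing where recording practice already covers the case.

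**What to change.** Add to 7.1.5.1: *or any AE with onset before first dose that increases in CTCAE grade on or after first dose and within the same window*. Add the matching rule to 7.1.5.2: such an event is dated at the grade increase where that date is recorded. The SAP does not say whether this date is collected, so 7.1.5.2 should also name the convention used when it is absent. Carry the resulting flag into the AE-of-interest and safety-topic tables (7.1.7.3, 7.1.7.4), including their breakdown by onset time.

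Keep the clause to grade increase, which is the criterion missing next to the DLT and laboratory rules. Where each grade increase is already a new AE record with its own onset date, the clause changes no count.

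The cost is one clause and one programming rule, plus a check of AEs with pre-dose onset in small cohorts. The downside is comparability. The primary analysis has been run (Section 2.2) and this SAP version serves the final synoptic CSR (Section 13), so final counts may rise slightly and differ from the primary-analysis tables and from the sister magrolimab studies. The CSR should say so. Section 1 already provides for documenting changes after SAP finalization there.
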